9.3.3 Procedure for the handling of discontinued subjects

9.3.3.1 Handling of subjects who discontinued from the trial

The principal investigator must document any discontinuation of a subject and inform the sponsor. Where applicable, the relevant IECs must be informed with a detailed written explanation.

The following must be done for **all** discontinued subjects, including those who withdrew informed consent:

- Document the main reason for discontinuation from the trial.
- Ensure that all data collected until the day of discontinuation is transferred to the CRF.
- Ensure that any dispensed pain assessment booklet is returned.
- Ensure that any unused IMPs and rescue medication (including all packaging) is returned.
- If possible, perform all tests as defined for the End-of-treatment Visit (Visit 3).
- Complete any other trial-related formalities, e.g., those related to discharge from the trial site.
- For subjects withdrawing consent, document in the source data the date and time of withdrawal.
- Document in writing, if a subject withdraws consent but agrees to attend the End-of-treatment Visit (Visit 3) and the Final Visit (Visit 4).

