10.5 Rescue medication

Details on rescue medication are provided in Section 1.4.2.

Subjects can request and take rescue medication at any time after the first administration of the IMPs if their trial medication does not provide sufficient pain relief. However, they will be encouraged (but not required) to refrain from rescue medication intake until at least 120 minutes after the intake of the first dose of IMPs (i.e., until diclofenac and tramadol have reached their maximum plasma concentration) to be able to reliably assess the efficacy of the IMPs first.

The time will be registered when subjects first request rescue medication and the time they take their first dose. Subjects taking rescue medication will be asked to complete the trial procedures as planned.

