9.3 Secondary Efficacy Analyses

The analysis of the following list of the secondary endpoints is given below:

1. Total Pain Relief at 6 hours (TOTPAR6), 8 hours (TOTPAR8) post-dose
2. Summed Pain Intensity Difference (SPID) at 4, 6, 8, and 24 hours after first dose
3. Time to achieve a 50% reduction of baseline pain (pain at least half gone)
4. Time to onset of first perceptible pain relief (stopwatch 1)
5. Time to onset of meaningful pain relief (stopwatch 2)
6. Time to intake of first rescue medication dose
7. Subject's global evaluation of the treatment (5-point Likert Scale; 0 poor to 4 excellent) at 8 hours after the first dose of IMPs or before first intake of rescue medication (whichever was first) and at 24 hours after the first dose of IMPs

TOTPARs and SPIDs at each of their summary time points will be analyzed using the same ANCOVA model described for the primary endpoint. Note that alpha levels for secondary analyses are not adjusted for multiple comparisons.

The time to onset of event endpoints will be presented using Kaplan-Meier plots. Medians will be compared across the groups using Wilcoxon Log-rank test, and Hazard Ratios (HR) will be compared across the groups using Cox Hazard Ratio model. Time to onset will be defined as date/time from the first administration of IMPs to the date/time when the subject first reports the event (50% reduction of baseline pain, perceptible pain relief, meaningful pain relief, and intake of rescue medication – each separately). The summaries will include quartiles and HR and their corresponding 95% confidence intervals. Please see [Appendix B](#) for details on the determination of event and censoring time points.

Note that alpha levels for secondary analyses are not adjusted for multiple comparisons.

Subject's global assessment of the treatment will also be summarized with descriptive statistics (patient counts and percentages for each assessment category) at 8 and 24 hours.

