9.4 Exploratory Efficacy Analyses

The following exploratory analyses will be performed on these additional efficacy outcomes:

1. Pain Relief Score after first dose over time
2. Pain Intensity Score after the first dose over time (based on NRS)
3. Pain Intensity Difference (PID, NRS) after first dose over time
4. Peak pain relief score
5. Peak pain intensity difference
6. Time to request the first dose of rescue medication
7. Time to peak pain relief score
8. Time to peak pain intensity difference

Pain relief scores, pain intensity scores, and pain intensity difference scores over time will be analyzed at each time point using the same ANCOVA model described for the primary endpoint, TOTPAR4. Peak pain relief score and peak pain intensity difference will also be analyzed using the same ANCOVA model described for the primary endpoint.

Time to peak pain relief score and time to peak pain intensity difference be presented using Kaplan-Meier plots. Medians will be compared across the groups using Wilcoxon Log-rank test, and Hazard Ratios (HR) will be compared across the groups using Cox Hazard Ratio model. The summaries will include quartiles and HR and their corresponding 95% confidence intervals along with the p-values. Please see [Appendix B](#) for details on the determination of event and censoring time points. Note that alpha levels for exploratory analyses are not adjusted for multiple comparisons.

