The day/actual time of ibuprofen (and of ketorolac if needed) request and the day/actual time and amount of ibuprofen intake (or ketorolac administration) will be documented in the CRF and the source document(s). The time from administration of IMP to the first dose of rescue medication will be calculated.

12. Time to Peak Pain Relief and Peak Pain Intensity Difference Scores

The first day/time where the subject reaches their maximum pain relief and their maximum pain intensity difference, as described in items 4 and 7 above, respectively, will be considered the event times for these two endpoints.

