Appendix B: Rules for Censoring in Time to Event Analyses

Below are the detailed rules for determining the time of the event and the censoring times for the various time-to-event analyses to be performed for this study.

Time-to-Event Variable	Event Time Point	Censor Time Point
Time to achieve a 50% reduction of baseline pain	The first time point where pain half gone is indicated, prior to the use of any rescue medication.	Subjects without events are censored at the earlier of the time of their first use of rescue medication and the time of their last, non-missing pain half gone assessment.
Time to onset of first perceptible pain relief*	The time when perceptible pain relief stopwatch is stopped, prior to the use of any rescue medication.	Subjects without events (as indicated by checking the “no” perceptible pain relief box or taking rescue medication prior to the occurrence of perceptible pain relief) are censored at the earlier of the time of their first use of rescue medication, the minutes/seconds entered for time of perceptible pain relief (which is when the stopwatch was stopped and so no longer assessed), and 8 hours.
Time to onset of meaningful pain relief*	The time when meaningful pain relief stopwatch is stopped, prior to the use of any rescue medication.	Subjects without events (as indicated by checking the “no” meaningful pain relief box or taking rescue medication prior to the occurrence of meaningful pain relief) are censored at the earlier of the time of their first use of rescue medication, the minutes/seconds entered for time of meaningful pain relief (which is when the stopwatch was stopped and so no longer assessed), and 8 hours.
Time to intake of first rescue medication dose	The time of first intake of rescue medication within 24 hours of first dose.	Subjects without events are censored at the time of their 24 hour global assessment (at the time when rescue meds were to be turned in), and if one did not take place, then at 24 hours (i.e., when subjects were to turn in their unused rescue medication as Visit 3).
Time to request the first dose of rescue medication	The time of the first request for rescue medication within 24 hours of first dose.	Subjects without events are censored at the time of their 24 hour global assessment (at the time when rescue meds were to be turned in), and if one did not take place, then at 24 hours (i.e., when subjects were to turn in their unused rescue medication as Visit 3).

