Time to peak pain relief score	The first time point where the subject experiences their peak pain relief score among assessments made prior to use of any rescue medication.	All subjects with post-baseline assessments have events – there is no censoring.
Time to peak pain intensity difference score	The first time point where the subject experiences their peak pain intensity difference score, among assessments made prior to use of any rescue medication.	All subjects with post-baseline assessments have events – there is no censoring.

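### The two time-to-peak rules in SAP Appendix B count a subject with no relief as having peaked, on the relief scale at 15 minutes, so treatment failure enters the exploratory hazard ratio as speed

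*SAP*

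**What the plan says.** SAP Appendix A (items 4 and 7) defines peak relief as the highest score on the 0 to 4 relief scale over 16 hours, and peak PID as the largest difference from baseline over 24 hours. Both use only assessments before any rescue medication. Item 12 sets the event time: "The first day/time where the subject reaches their maximum pain relief and their maximum pain intensity difference". Relief and pain intensity are first scored 15 minutes after dosing.

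For both time-to-peak endpoints the censoring column of SAP Appendix B reads "All subjects with post-baseline assessments have events" and adds that nobody is censored. Neither appendix sets a smallest value that qualifies as a peak.

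SAP 9.4 lists both endpoints as exploratory, without multiplicity adjustment. It plans Kaplan-Meier plots, a Wilcoxon/log-rank comparison and a Cox model: "The summaries will include quartiles and HR and their corresponding 95% confidence intervals along with the p-values". The peak scores themselves are analysed separately by ANCOVA. SAP section 11 records that these endpoints were added in the SAP.

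The three onset endpoints (pain half gone, perceptible relief, meaningful relief) follow a different rule. For pain half gone, Appendix B says "Subjects without events are censored at the earlier of the time of their first use of rescue medication" or the last assessment. The two stopwatch endpoints are likewise censored at rescue, and at 8 hours at the latest. SAP 9.3 states "The time to onset of event endpoints will be presented using Kaplan-Meier plots".

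**The concern.** Time to peak is read as speed of action, with shorter times better. Under these rules a subject who never gets any relief has a maximum of 0, first reached at the first assessment, and so gets the best possible time. A subject with real relief that builds to its maximum at 2 hours gets a worse one. An arm with more complete failures gains early events, and the hazard ratio moves in its favour.

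At stake is the direction of two exploratory hazard ratios and their p-values, which could be cited in the report as evidence about speed of effect.

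**Working it through.** **Tracing the rule.** Take a subject with relief 0 at 15, 30, 45, 60 and 90 minutes who then takes rescue. The pre-rescue maximum is 0, it first occurs at 0.25 h, and the rule records an event at 0.25 h. This needs a recorded 15-minute score; otherwise the event falls at the first recorded score. On PID, a subject whose pain stays at or above baseline has a maximum of 0 or less, and the event falls at whichever assessment was least bad. If pain is unchanged from the start, that is again 15 minutes.

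**Inputs.** The documents state no rate of non-response and no figure for these endpoints, so there is nothing to reproduce. From the documents: 180 evaluable subjects per arm (SAP section 4) and a first assessment at 0.25 h. Assumed: responders peak with equal probability at 1, 1.5, 2, 3 or 4 h in both arms, and a share z of subjects score 0 throughout.

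**Cumulative share with an event.**
- SAP rule: z at 0.25 h, then z + (1 − z) × k/5 at the k-th responder time.
- Zero-relief subjects as non-events: (1 − z) × k/5.

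| Time (h) | SAP, z = 15% | SAP, z = 5% | Non-event, z = 15% | Non-event, z = 5% |
|---|---|---|---|---|
| 0.25 | 15% | 5% | 0% | 0% |
| 1 | 32% | 24% | 17% | 19% |
| 1.5 | 49% | 43% | 34% | 38% |
| 2 | 66% | 62% | 51% | 57% |
| 3 | 83% | 81% | 68% | 76% |
| 4 | 100% | 100% | 85% | 95% |

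Under the SAP rule the worse arm leads at every time before 4 h, although its responders are no faster. With failures as non-events it trails at every time from 1 h on. The median is 2 h in all four columns, so the medians alone would not reveal the problem.

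**Hazard ratio, worse arm against better arm** (simulated trials of 180 per arm, Cox with Efron ties; non-events carried to 16 h):

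| All-zero share | Responder timing | SAP rule | Non-event coding |
|---|---|---|---|
| 10% vs 10% | same | 1.00 | about 1.0 |
| 15% vs 5% | same | 1.11 | 0.75 |
| 30% vs 10% | same | about 1.25 | 0.60 |

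With the same timing, the worse arm is significantly faster (two-sided 5%) at 15% vs 5% in 24 to 25% of trials by log-rank and 38 to 39% by Gehan-Wilcoxon. At 30% vs 10% the figures are 69 to 71% and 91 to 92%. Under non-event coding this never happens at either pair of shares.

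**Varying the timing.** Let responders in the better arm peak slightly sooner, with probabilities 0.25, 0.25, 0.20, 0.15, 0.15. Their mean is 0.25 + 0.375 + 0.40 + 0.45 + 0.60 = 2.075 h, against 11.5/5 = 2.30 h. The SAP-rule hazard ratio is then about 0.95 at 15% vs 5%, with significance for the worse arm in about 1% (log-rank) and 3% (Wilcoxon) of trials. At 30% vs 10% it is about 1.09. The opposite shift raises the 15% vs 5% value to about 1.3.

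The simulation covers the relief scale only. For PID the point rests on the mechanism.

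**The case against.** The endpoints are exploratory, unadjusted and additional to the protocol, and the peak-score ANCOVA would show the failures. That is right and sets the weight of the point. It does not repair a hazard ratio that counts failure as speed.

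The illustration depends on equal responder timing. This also stands. A reader might infer that the rule always reverses the comparison. The documents do not support that: they give no failure rates, and a modest timing advantage in the better arm takes the hazard ratio from 1.11 to about 0.95.

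The recoding is not neutral either. With identical responder timing it gives 0.75, which reflects non-response and not speed. That is why the result has to be read beside the peak score.

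A reader might also infer that censoring at rescue makes the onset analyses invalid. It does not. Log-rank and Cox remain valid cause-specific comparisons. With true onset of 75% vs 50% in an illustration where only never-responders take rescue, the Cox hazard ratio is 1.86 to 1.90 under the planned rule and 1.89 to 1.90 with rescuers carried as non-events. Only the Kaplan-Meier plateau and upper quantiles can be misread as the share reaching onset. With rescue spread over 1–4, 2–4 or 2–6 h (the Protocol has subjects "encouraged (but not required) to refrain from rescue medication intake until at least 120 minutes"), a true 50% shows as 51.0 to 63.3% at 8 h when half to 90% of never-responders rescue. The gap is larger if later responders also rescue. Replacing the prespecified quartiles would be a change of estimand, not the correction of an error. The two stopwatch rows also carry an asterisk whose footnote is not visible in the supplied text and may qualify them.

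Last, a reader might object that a subject with no recorded rescue and no 24-hour global assessment is censored at 24 hours in the rescue endpoints. Assuming 50% rescue by 24 h at constant hazard and loss uniform over 8 to 24 h, the bias is 13.6 points × the share lost: 0.1 points at 1% and 0.7 at 5%. That is negligible and not part of this point.

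**Conclusion.** The point holds for the two time-to-peak endpoints, as a minor one. The text sets no minimum and no censoring, so complete failures are counted as events, at the earliest possible time on the relief scale. The direction of the bias, toward the arm with more failures, follows from the rule. Its size does not: the illustrative hazard ratio at 15% vs 5% runs from about 0.95 to about 1.3 as responder timing varies, and all of these rates are assumed. Confidence is high for the mechanism and low for the magnitude. For the onset endpoints there is room only for a descriptive addition. Neither TOTPAR4 nor the Holm procedure uses these rules, so the primary conclusion does not depend on them.

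**What to change.** Before database lock, change the two time-to-peak rows of SAP Appendix B and align Appendix A item 12:

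- Do not count a peak relief of 0, or a peak PID of 0 or less, as an event.
- Carry such subjects who took rescue as non-events to 16 h (relief) or 24 h (PID).
- Censor such subjects who left early at their last assessment.
- State that the result is read beside the peak score, because the hazard ratio then mixes response with speed. The repair is partial: an early rescuer with a low but positive peak still looks fast.

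This needs no new data and only a small programming change.

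Optional and descriptive: for the three onset endpoints, add a cumulative-incidence curve with pre-onset rescue as a competing event beside the planned Kaplan-Meier plot, and label the hazard ratios cause-specific. The planned log-rank and Cox analyses stay as they are. The cost is a sentence in SAP 9.3 and three more entries in the Appendix C figure list.

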Appendix C: List of Tables, Figures, and Listings

List of Tables

Table Number	Table Description
14.1.1.1	Subject Disposition (All Subjects)
14.1.1.2	Subject Disposition by Site (All Subjects)
14.1.2.1	Early Discontinuation of Study Drug by Time Period (Safety Set)
14.1.2.2	Early Discontinuation of Study Drug by Time Period (FAS)
14.1.3	Protocol Deviations (FAS)
14.1.4.1	Demographic and Baseline Characteristics (Safety Set)
14.1.4.2	Demographic and Baseline Characteristics (FAS)
14.1.4.3	Demographic and Baseline Characteristics (PPS)
14.1.5.1	Medical History at Baseline (Safety)
14.1.5.2	Medical History at Baseline (FAS)
14.1.5.3	Medical History at Baseline (PPS)
14.1.6	Physical Examination at Baseline (Safety Set)
14.1.7.1	Prior Medications (Safety Set)
14.1.7.2	Prior Medications (FAS)
14.1.7.3	Prior Medications (PPS)
14.1.8.1	Concomitant Medications (Safety Set)
14.1.8.2	Concomitant Medications (FAS)
14.1.8.3	Concomitant Medications (PPS)
14.1.9.1	Study Drug Exposure (Safety Set)
14.2.1.1	Total Pain Relief through 4 Hours (TOTPAR4) (LOCF and Delta Substitution) (FAS)
14.2.1.2	Total Pain Relief through 4 Hours (TOTPAR4) (LOCF and Delta Substitution) (PPS)
14.2.1.3	Total Pain Relief through 4 Hours (TOTPAR4) (LOCF Only) (FAS)
14.2.1.4	Total Pain Relief through 4 Hours (TOTPAR4) (LOCF and Zero Substitution) (FAS)
14.2.1.5	Total Pain Relief through 4 Hours (TOTPAR4) (WOCF and LOCF) (FAS)
14.2.1.6	Total Pain Relief through 4 Hours (TOTPAR4) (WOCF Only) (FAS)
14.2.2.1	Total Pain Relief through 6 Hours (TOTPAR6) (LOCF and Delta Substitution) (FAS)
14.2.2.2	Total Pain Relief through 6 Hours (TOTPAR6) (LOCF and Delta Substitution) (PPS)
14.2.2.3	Total Pain Relief through 6 Hours (TOTPAR6) (LOCF Only) (FAS)
14.2.2.4	Total Pain Relief through 6 Hours (TOTPAR6) (LOCF and Zero Substitution) (FAS)
14.2.2.5	Total Pain Relief through 6 Hours (TOTPAR6) (WOCF and LOCF) (FAS)
14.2.2.6	Total Pain Relief through 6 Hours (TOTPAR6) (WOCF Only) (FAS)

Table Number	Table Description
14.2.3.1	Total Pain Relief through 8 Hours (TOTPAR8) (LOCF and Delta Substitution) (FAS)
14.2.3.2	Total Pain Relief through 8 Hours (TOTPAR8) (LOCF and Delta Substitution) (PPS)
14.2.3.3	Total Pain Relief through 8 Hours (TOTPAR8) (LOCF Only) (FAS)
14.2.3.4	Total Pain Relief through 8 Hours (TOTPAR8) (LOCF and Zero Substitution) (FAS)
14.2.3.5	Total Pain Relief through 8 Hours (TOTPAR8) (WOCF and LOCF) (FAS)
14.2.3.6	Total Pain Relief through 8 Hours (TOTPAR8) (WOCF Only) (FAS)
14.2.4.1	Total Pain Relief through 4 Hours (TOTPAR4) (LOCF and Delta Substitution) (FAS in Subjects with Moderate Pain Intensity)
14.2.4.2	Total Pain Relief through 4 Hours (TOTPAR4) (LOCF and Delta Substitution) (FAS in Subjects with Severe Pain Intensity)
14.2.5.1	Total Pain Relief through 4 hours (TOTPAR4) by Site (LOCF and Delta Substitution) (FAS)
14.2.5.2	Total Pain Relief through 4 hours (TOTPAR4) by Site (LOCF and Delta Substitution) (PPS)
14.2.5.3	Total Pain Relief through 6 hours (TOTPAR6) by Site (LOCF and Delta Substitution) (FAS)
14.2.5.4	Total Pain Relief through 6 hours (TOTPAR6) by Site (LOCF and Delta Substitution) (PPS)
14.2.5.5	Total Pain Relief through 8 hours (TOTPAR8) by Site (LOCF and Delta Substitution) (FAS)
14.2.5.6	Total Pain Relief through 8 hours (TOTPAR8) by Site (LOCF and Delta Substitution) (PPS)
14.2.6.1	Pain Relief Score after First Dose over Time (FAS)
14.2.6.2	Pain Intensity Score after First Dose over Time (FAS)
14.2.6.3	Pain Intensity Difference (PID) after First Dose over Time (FAS)
14.2.6.4	Summed Pain Intensity Difference (SPID) after First Dose over Time (FAS)
14.2.7.1	Peak Pain Relief Score (FAS)
14.2.7.2	Peak Pain Intensity Difference (FAS)
14.2.8.1	Time to Achieve a 50% Reduction of Baseline Pain (FAS)
14.2.8.2	Time to Onset of First Perceptible Pain Relief (FAS)
14.2.8.3	Time to Onset of Meaningful Pain Relief (FAS)
14.2.8.4	Time to Request of First Rescue Medication (FAS)
14.2.8.5	Time to Intake of First Rescue Medication (FAS)
14.2.8.6	Time to Peak Pain Relief Score (FAS)
14.2.8.7	Time to Peak Pain Intensity Difference Score (FAS)
14.2.9.1	Subject's Global Evaluation of the Treatment (FAS)
14.3.1.1	Overall Summary of All Adverse Events (Safety Set)
14.3.1.2	Treatment-Emergent Adverse Events by System Organ Class and Preferred Term (Safety Set)

Table Number	Table Description
14.3.1.3	Non Treatment-Emergent Adverse Events by System Organ Class and Preferred Term (Safety Set)
14.3.1.4	Treatment-Emergent Adverse Events by System Organ Class, Preferred Term and Severity (Safety Set)
14.3.1.5	Treatment-Emergent Adverse Events by System Organ Class, Preferred Term and Relationship to IMP or Rescue Medication (Safety Set)
14.3.1.6	Treatment-Emergent Severe Adverse Events by System Organ Class and Preferred Term (Safety Set)
14.3.1.7	Treatment-Emergent Adverse Events Leading to Dose Reduction by System Organ Class and Preferred Term (Safety Set)
14.3.1.8	Treatment-Emergent Adverse Events Leading to Dose Interruption by System Organ Class and Preferred Term (Safety Set)
14.3.1.9	Treatment-Emergent Adverse Events Leading to Study Drug Withdrawal by System Organ Class and Preferred Term (Safety Set)
14.3.1.10	Treatment-Emergent Adverse Events Leading to Dose Reduction, Dose Interruption, or Study Drug Withdrawal by System Organ Class and Preferred Term (Safety Set)
14.3.1.11	Pre-Treatment Adverse Events by System Organ Class and Preferred Term (Safety Set)
14.3.1.12	Day 1 Treatment Emergent Adverse Events by System Organ Class and Preferred Term (Safety Set)
14.3.1.13	Post-Treatment Adverse Events by System Organ Class and Preferred Term (Safety Set)
14.3.1.14	Treatment-Emergent Adverse Events by SOC and Preferred Term (Safety Set Subgroup: Age < median)
14.3.1.15	Treatment-Emergent Adverse Events by SOC and Preferred Term (Safety Set Subgroup: Age ≥ median)
14.3.1.16	Treatment-Emergent Adverse Events by SOC and Preferred Term (Safety Set Subgroup: Female)
14.3.1.17	Treatment-Emergent Adverse Events by SOC and Preferred Term (Safety Set Subgroup: Male)
14.3.1.18	Treatment-Emergent Adverse Events by SOC and Preferred Term (Safety Set Subgroup: Mestizo)
14.3.1.19	Treatment-Emergent Adverse Events by SOC and Preferred Term (Safety Set Subgroup: Non-Mestizo)
14.3.1.20	Treatment-Emergent Adverse Events by SOC and Preferred Term (Safety Set Subgroup: Baseline Pain Intensity Moderate)
14.3.1.21	Treatment-Emergent Adverse Events by SOC and Preferred Term (Safety Set Subgroup: Baseline Pain Intensity Severe)
14.3.1.22	Treatment-Emergent Adverse Events by SOC and Preferred Term (Safety Set Subgroup: Using Concomitant Medication at Any Time During the Study)
14.3.1.23	Treatment-Emergent Adverse Events by SOC and Preferred Term (Safety Set Subgroup: Not Using Concomitant Medication at Any Time During the Study)

Table Number	Table Description
14.3.1.24	Treatment-Emergent Adverse Events by SOC and Preferred Term in at least 20% of Subjects in any Treatment Group (Safety Set)
14.3.2.1	Treatment-Emergent Serious Adverse Events by System Organ Class and Preferred Term (Safety set)
14.3.2.2	Treatment-Emergent Fatal Serious Adverse Events by System Organ Class and Preferred Term (Safety Set)
14.3.2.3	Treatment-Emergent Non-Fatal Serious Adverse Events by System Organ Class and Preferred Term (Safety Set)
14.3.4.1	Hematology Values at Enrollment Visit Conventional Units (Safety Set)
14.3.4.2	Hematology Values at Enrollment Visit SI Units (Safety Set)
14.3.4.3	Serum Chemistry Values at Enrollment Visit Conventional Units (Safety Set)
14.3.4.4	Serum Chemistry Values at Enrollment Visit SI Units (Safety Set)
14.3.4.5	Urinalysis pH and Specific Gravity (Safety Set)
14.3.4.6	Urinalysis Categorical Lab Parameters (Safety Set)
14.3.4.7	Serum Coagulation Values at Enrollment Visit Conventional Units (Safety Set)
14.3.4.8	Serum Coagulation Values at Enrollment Visit - SI Units (Safety Set)
14.3.5.1	Vital Signs Enrollment Visit and Allocation Visit (Safety Set)

List of Figures

Figure Number	Figure Description
14.2.10.1	Least Squares Mean Score in Total Pain Relief (TOTPAR) over Time (FAS)
14.2.10.2	Least Squares Mean Score in Pain Relief Score over Time (FAS)
14.2.10.3	Least Squares Mean Score in Pain Intensity Score over Time (FAS)
14.2.10.4	Least Squares Mean Score in Pain Intensity Difference (PID) over Time (FAS)
14.2.10.5	Least Squares Mean Score in Summed Pain Intensity Difference (SPID) over Time (FAS)
14.2.10.6	Kaplan-Meier Curves for Time to Achieve a 50% Reduction of Baseline Pain (FAS)
14.2.10.7	Kaplan-Meier Curves for Time to Onset of First Perceptible Pain Relief (FAS)
14.2.10.8	Kaplan-Meier Curves for Time to Onset of Meaningful Pain Relief (FAS)
14.2.10.9	Kaplan-Meier Curves for Time to Request of First Rescue Medication (FAS)
14.2.10.10	Kaplan-Meier Curves for Time to Intake of First Rescue Medication (FAS)
14.2.10.11	Kaplan-Meier Curves for Time to Peak Pain Relief Score (FAS)
14.2.10.12	Kaplan-Meier Curves for Time to Peak Pain Intensity Difference (PID) Score (FAS)

List of Data Listings

Listing Number	Listing Description
16.2.1.1	Subject Disposition
16.2.1.2	Informed Consent
16.2.1.3	Withdrawal of Consent
16.2.2.1	Protocol Deviations
16.2.2.2	Inclusion/Exclusion Findings
16.2.3	Subject Populations
16.2.4.1	Demographics and Baseline Characteristics (Part 1 of 2)
16.2.4.2	Demographics and Baseline Characteristics (Part 2 of 2)
16.2.4.3	Dental History at Screening
16.2.4.4	Medical History at Screening
16.2.4.5	Physical Examination at Screening
16.2.4.6	Radiological Examination
16.2.4.7	Dental Surgery (Part 1 of 2)
16.2.4.8	Dental Surgery (Part 2 of 2)
16.2.4.9	Urine Pregnancy Test
16.2.4.10	Prior Medications
16.2.4.11	Concomitant Medications
16.2.5.1	Study Drug Administration
16.2.5.2	IMP-Drug Accountability
16.2.5.3	Rescue Medication
16.2.5.4	Rescue Medication-Drug Accountability
16.2.6.1	Pain Intensity (NRS)
16.2.6.2	Pain Relief (5-point VRS)
16.2.6.3	Pain at Least Half Gone
16.2.6.4	Global Evaluation of Treatment
16.2.7.1	Adverse Events
16.2.7.2	Treatment-Emergent Serious Adverse Events (Collected on AE CRF)
16.2.7.3	Fatal Treatment-Emergent Serious Adverse Events (Collected on AE CRF)
16.2.7.4	Non-Fatal Treatment-Emergent Serious Adverse Events (Collected on AE CRF)
16.2.8.1	Local Laboratory Normal Ranges Conventional Units
16.2.8.2	Local Laboratory Normal Ranges SI Units
16.2.8.3	Hematology Conventional Units (Part 1 of 2)
16.2.8.4	Hematology Conventional Units (Part 1 of 2)
16.2.8.5	Hematology SI Units (Part 1 of 2)
16.2.8.6	Hematology SI Units (Part 1 of 2)
16.2.8.7	Serum Chemistry Conventional Units (Part 1 of 2)
16.2.8.8	Serum Chemistry Conventional Units (Part 1 of 2)
16.2.8.9	Serum Chemistry SI Units (Part 1 of 2)
16.2.8.10	Serum Chemistry SI Units (Part 1 of 2)

Listing Number	Listing Description
16.2.8.11	Urinalysis
16.2.8.12	Coagulation
16.2.9.1	Vital Signs
16.2.9.2	Vital Sign Results of Potential Clinical Significance
16.2.9.3	Subject Visit Dates
16.2.9.4	Follow up
